4.2 Timing of interim analyses and design adaptations

Not applicable.

4.3 Definition of end of study

Completion of this study as a whole will occur upon the availability and accuracy verification of the last data point (Visit 28) required for statistical analysis.

Refer to Section 7.1 for details.

4.4 Early study termination

The study can be terminated at any time for any reason by Novartis. Should this be necessary, the patient should be seen as soon as possible and the same assessments should be performed as described in Section 7 for a prematurely withdrawn patient. The investigator may be informed of additional procedures to be followed in order to ensure that adequate consideration is given to the protection of the patient's interests. The investigator will be responsible for informing IRBs and/or IECs of the early termination of the trial.

5 Population

5.1 Patient population

The study population will consist of patients aged 10 years or older, male or female with transfusion-dependent thalassemia or MDS at very low, low or intermediate risk recruited at all Region Europe participating sites that have completed the 24-week treatment under protocol CICL670F2201 and who have been randomized to the FCT formulation or to the DT formulation. Patients who will have withdrawn prematurely from CICL670F2201 will not be enrolled. Patients with a lag period between completion of CICL670F2201 and enrollment in this study can still be enrolled even if they had to switch to DT or other chelation therapy in this period, following washout.

The investigator or designee must ensure that only patients who meet all the following inclusion and none of the exclusion criteria are offered treatment in the study.

5.2 Inclusion criteria

Patients eligible for inclusion in this study have to meet all of the following criteria:

- Have completed 24-weeks of study treatment as described in protocol CICL670F2201.
- Are deemed to be tolerating deferasirox treatment by the investigator.
- Provided written informed consent/assent before any study-specific procedures are performed. For pediatric patients, consent will be obtained from parent(s) or legal patient's representative. Investigators will also obtain assent of patients according to local, regional or national guidelines.
- Are deemed to be tolerating deferasirox treatment by the investigator if continuing directly from protocol CICL670F2201.

The inclusion criteria in study CICL670F2201 were stated as follows:

- 1. Written informed consent/assent before any study-specific procedures. For pediatric patients, consent will be obtained from parent(s) or legal patient's representative. Investigators will also obtain assent of patients according to local, regional or national guidelines.
- 2. Male and female patients aged ≥ 10 years
- 3. Patients with transfusion-dependent thalassemia and iron overload, requiring deferasirox DT at doses of ≥ 30 mg/kg/day as per the investigator's decision, OR

Patients with very low, low or intermediate (int) risk myelodysplastic syndrome (MDS) and iron overload, requiring deferasirox DT at doses of ≥ 20 mg/kg/day as per the investigator's decision.

- The very low, low or intermediate (int) risk MDS should be determined by the Revised International Prognostic Scoring System (IPSS-R) and IPSS-R must be confirmed by a bone marrow examination within 6 months prior to study entry and must be hematologically stable with a patient's life expectancy of at least 1 year.
- 4. History of transfusion of at least 20 packed red blood cells (PRBC) units and anticipated to be transfused with at least 8 units of PRBCs annually during the study
- 5. Serum ferritin > 1000 ng/mL, measured at Screening Visit 1 and Screening Visit 2 (the mean value will be used for eligibility criteria).

5.3 Exclusion criteria

Patients eligible for this study must not meet **any** of the exclusion criteria defined for study CICL670F2201, which were as follows:

- 1. Creatinine clearance below the contraindication limit in the locally approved prescribing information. Creatinine clearance will be estimated from serum creatinine at Screening Visit 1 and Screening Visit 2 and the mean value will be used for eligibility criteria.
- 2. Serum creatinine > 1.5 × upper limit of normal range (ULN) at Screening measured at Screening Visit 1 and Screening Visit 2 (the mean value will be used for eligibility criteria).
- 3. Alanine aminotransferase (ALT)/serum glutamic pyruvic transaminase (SGPT) > 5 × ULN, unless liver iron concentration (LIC) confirmed as > 10 mg Fe/dw within 6 months prior to Screening Visit 1.
- 4. Significant proteinuria as indicated by a urinary protein/creatinine ratio > 0.5 mg/mg in a non-first void urine sample at Screening Visit 1 or Screening Visit 2.
- 5. Patients with significant impaired gastrointestinal function or gastrointestinal disease that may significantly alter the absorption of oral deferasirox (e.g. ulcerative diseases, uncontrolled nausea, vomiting, diarrhea, malabsorption syndrome, or small bowel resection).
- 6. Clinical or laboratory evidence of active Hepatitis B or Hepatitis C (Hepatitis B surface Antigen (HBsAg) in the absence of Hepatitis B surface antibody (HBsAb) or HCV antibody positive with HCV RNA positive).

- 7. Patients with psychiatric or addictive disorders which prevent them from giving their informed consent or undergoing any of the treatment options or patients unwilling or unable to comply with the protocol.
- 8. Patients with a known history of HIV seropositivity (Elisa or Western blot).
- 9. History of malignancy of any organ system, treated or untreated, within the past 5 years whether or not there is evidence of local recurrence or metastases, with the exception of localized basal cell carcinoma of the skin.
- 10. Patients participating in another clinical trial or receiving an investigational drug.
- 11. History of hypersensitivity to any of the study drug or excipients.
- 12. Significant medical condition interfering with the ability to partake in this study (e.g. systemic uncontrolled hypertension, unstable cardiac disease not controlled by standard medical therapy, systemic disease (cardiovascular, renal, hepatic, etc.).
- 13. Women of child-bearing potential, defined as all women physiologically capable of becoming pregnant, unless they are using effective methods of contraception during dosing of study treatment. Effective contraception methods include:
 - Total abstinence (when this is in line with the preferred and usual lifestyle of the patient. Periodic abstinence (e.g., calendar, ovulation, symptothermal, post-ovulation methods) and withdrawal are not acceptable methods of contraception.
 - Female sterilization (have had surgical bilateral oophorectomy with or without hysterectomy) or tubal ligation at least 6 weeks before taking study treatment. In case of oophorectomy alone, only when the reproductive status of the woman has been confirmed by follow-up hormone level assessment.
 - Male partner sterilization (at least 6 months prior to screening). For female patients on the study, the vasectomized male partner should be the sole partner for that patient.
 - Barrier methods of contraception: Condom or Occlusive cap (diaphragm or cervical/vault caps) with spermicidal foam/gel/film/cream/ vaginal suppository.
 - Placement of an intrauterine device or intrauterine system.
 Please note that deferasirox may reduce the efficacy of hormonal contraception thus it is recommended to use alternative methods of contraception as described above.
 Women are considered post-menopausal and not of child bearing potential if they have had 12 months of natural (spontaneous) amenorrhea with an appropriate clinical profile (e.g. age appropriate, history of vasomotor symptoms) or have had surgical bilateral oophorectomy (with or without hysterectomy) or tubal ligation at least six weeks ago. In the case of oophorectomy alone, only when the reproductive status of the woman has been confirmed by follow-up hormone level assessment is she considered not of child bearing potential.
- 14. For prohibited medication please refer to Section 6.4.3.
- 15. Liver disease with severity of Child-Pugh Class B or C.

6 **Treatment**

Novartis

6.1 Study treatment

The sponsor will provide the following open label study medication:

• Deferasirox FCT will be provided as 90 mg, 180 mg and 360 mg film-coated tablets for oral use.

6.1.1 Dosing regimen

Having completed the 24 weeks of CICL670F2201, patients recruited at Region Europe participating sites will be invited to participate in this study to continue FCT or switch from DT to the FCT formulation. Patients completing CICL670F2201 and switching to commercially available DT or other ICT will still be eligible to enroll in this study after a 5-day washout period during the Screening period.

All patients randomized in the DT arm in CICL670F2201 and well-managed on treatment with deferasirox DT will use an equivalent FCT dose. Patient switching from DT will use an equivalent FCT dose at the start of this study corresponding to their DT dose at the end of CICL670F2201 (see Appendix 14.2). A patient who is receiving an adjusted dose at the time of completing CICL670F2201 will commence this study receiving that adjusted dose until a time when the investigator deems it necessary to adjust the dose. Patients who completed CICL670F2201 and had switched to commercially available DT or other ICT will have to undergo a 5-day washout period and will then be assigned FCT at a starting dose equivalent to their last deferasirox dose on CICL670F2201.

Dose adjustment for better treatment effects will be allowed every 3 months based on serum ferritin levels and the investigator's judgment. The dose adjustments will be performed in steps of 3.5 to 7 mg/kg/day for deferasirox FCT.

For each patient the daily dose is calculated by the physician based on the patient's actual body weight, and then rounded up or down to the nearest whole tablet according to the available strengths of deferasirox FCT tablets (90 mg, 180 mg and 360 mg, see Appendix 14.1). All doses planned and prescribed to the patient and all dose changes including reasons for change during the study must be recorded in the eCRF.

During the regular study visits, the investigator or pharmacist will dispense to the patient and/or legal patient representative, an appropriate number of deferasirox tablets depending on the patients calculated FCT dose. The number of tablets of each strength dispensed will be recorded in the Study Drug dosing Log. Each time the FCT deferasirox drug is dispensed to the patient and/or legal patient representative, the investigator will provide detailed instructions on how to prepare and administer the dose. Patients or legal patient representative will be instructed to take the assigned amount of study drug and will be obliged to return all unused study medication every month. Study medication returned by the patient will be counted and unused study medication will be recorded by the investigator/pharmacist involved in the study. Drug accountability will be noted by the field monitor during site visits and at the completion of the trial.

Medication labels will comply with the legal requirements of the countries where the study is implemented and be printed in the local language. They will supply no information about the patient. Only the patient identifier will be entered on the medication label by the investigator or pharmacist before the corresponding medication is handed out to the patient. The storage

Patients will swallow the required number of deferasirox FCT once per day either on an empty stomach or with a light meal (see Appendix 14.3 for examples on light meals).

It is recommended that the doses be timed such that they occur at almost the same time each day. For example, if the patient took the study medication at 10:00 AM on first day of treatment, the subsequent dose would also be taken at approximately 10:00 AM on the next day, and so on.

Deferasirox FCT dose adjustments based on safety are allowed at any time point in the study and will be in increments of 3.5-7 mg/kg/day. Throughout the study, the maximum dose of deferasirox FCT will be 28 mg/kg/day.

Table 6-1 Dose and treatment schedule for FCT formulation

conditions for study drug will be described on the medication label.

Study treatments	Pharmaceutical form and route of administration	Starting Dose	Dose adjustment	Max dose	Frequency and/or Regimen
Deferasirox	Film-coated tablets, per oral	Described in Section 6.1.1 (see Appendix 14.2 for guidance)	± 3.5 - 7 mg/kg/day	28 mg/kg/day	Once daily

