Data analysis	 Data from all centers participating in this study will be pooled for analyses. Standard descriptive analyses will include: Frequencies and percentages for categorical data; n, mean, standard deviation, minimum, median, 25th and 75th percentiles and maximum for continuous data. Detailed statistical analysis methods will be defined in statistical analysis plan documentation. 		
Key words	New formulation, deferasirox, film-coated tablet, chelation, iron overload, safety, long-term		

Amendment 1 (25-Oct-2017)

Amendment rationale

This protocol amendment is substantial and it is issued for the following reasons:

- The description related to study treatment duration in Protocol Summary, Section 4.1 (Description of study design), Section 6.1.5 (Treatment duration), and Section 7.1.3 (Treatment period) has been amended to clarify that there is no obligation for a subject to be withdrawn from the study upon local commercial availability of the FCT.
- As this study has its own CTA and EUDRACT numbers and is not, as such, an extension study, the references to "Core and Extension" study were removed throughout the protocol. However, enrolment is only open to patients who had completed CICL670F2201 study.
- In alignment with the Exjade prescribing information, deferasirox is contraindicated in patients with estimated creatinine clearance less than 60 mL/min (Section 6.3.1.2), immediate discontinuation of patient if severe cutaneous adverse reaction occurs (Section 6.3.1.5) and guidance on treating patients who develop moderate hepatic impairment (Child-Pugh Class B) (Section 6.3.1.6) during the trial is provided.
- In addition guidance was added regarding the concomitant administration of deferasirox with CYP1A2 substrate theophylline (Section 6.4.2), cholestyramine (Section 6.4.3) and drugs that have ulcerogenic potential (Section 6.4.4) in alignment with the Exjade prescribing information.
- To correct discrepancies on the description of the visit intervals between Table 7-1 (Visit evaluation schedule) and protocol text in Section 4.1 (Description of study design), Section 6.3.1.3 (Changes in serum ferritin), Section 7.1.3 (Treatment period), and Section 7.2.1 (Efficacy assessments).
- To clarify the following aspects in Section 6.1.1 (Dosing regimen):
 - Regarding patient's recruitment.

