 - Starting dose calculation for patients who completed CICL670F2201 study and switched to commercially available deferasirox dispersible tablet or other iron chelation therapy.
 - Timing of drug administration in accordance with the Investigator's brochure version 18.1.
- Clarification on drug supply disposal and destruction in Section 6.6.4.
- To correct the description for local clinical laboratory parameters collection plan (Hematology) described in Table 7-2 (Local clinical laboratory parameters collection plan).
- To remove reference related to collection of pregnancy outcomes for the pregnant partners of male patients in Section 8.4 (Pregnancies) in accordance with Novartis's pregnancy guidance working group.
- To clarify the demographic and other baseline data to be summarized descriptively in Section 10.2 in line with actual eCRF design. Specifically regarding:
 - Ethnicity

- ECG
- Audiometric test
- Ocular exam
- To correct the description for duration of treatment exposure, actual and planned daily dose in Section 10.3 (Treatments).
- Clarification on the descriptive statistical analyses of the primary objective in Section 10.4.2 (Statistical hypothesis, model, and method of analysis). Objectives were unchanged.
- To update description for supportive sensitivity analyses in Section 10.4.4.
- To add description for secondary efficacy objective analyses in Section 10.5.1.
- To update description for adverse events analyses in Section 10.5.2.1.

Changes to the protocol

Changes to specific sections of the protocol are shown in the track changes version of the protocol using strike through red font for deletions and red underline for insertions.

- Protocol summary (Study design): Corrected to "The study treatment duration of treatment will be for a maximum of 24 months".
- Section 1.2.1.1 (Clinical experience with deferasirox) and Section 2.6 (Risks and benefits): Updated "to align with the Exjade prescribing information".
- Section 4.1: Corrected to
 - Following enrollment (Visit 3/Day 1) patients will return to the site at 2 week intervals until Visit 5 (Month 1). Thereafter, scheduled visits will be monthly.
 - The planned duration of treatment in this study is for a maximum of 24 months.
 - In Figure 4-1 references to "Core and Extension" study were removed and undated to reflect changes based on the amendment rationale.
- Section 6.1.1: Amended to

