 - "Having completed the 24 weeks of CICL670F2201 study, patients recruited at Region Europe participating sites will be invited to participate in this study to continue FCT or switch from DT to the FCT formulation".
 - "Patients who completed CICL670F2201 study and had switched to commercially available DT or other ICT will have to undergo a 5-day washout period and will then be assigned FCT at a starting dose equivalent to their last deferasirox dose in CICL670F2201 study".
 - "Patients will swallow the required number of deferasirox FCT every day either on an empty stomach or with a light meal.
 - Removed reference related to "However, all patients should take their deferasirox FCT dose before 12:00 PM (noon)".
- Section 6.1.5: Corrected to "The duration of treatment in the current study is for a maximum of 24 months".
- Section 6.3.1.2: Added "Caution based on creatinine clearance".

- Protocol No. CICL670AIC04
- Section 6.3.1.3: Corrected to "Following enrollment (Visit 3/Day 1) serum ferritin will be monitored at 2 week intervals until Visit 5 (Month 1). Thereafter, scheduled assessments will be monthly".
- Section 6.3.1.5: added "Guidance regarding treatment discontinuation if severe cutaneous adverse reaction occurs".
- Section 6.3.1.6: added "Guidance related to dose modifications for patients with moderate hepatic impairment (Child-Pugh B)".
- Section 6.4.2: Added "Guidance related to concomitant use of deferasirox with CYP1A2 substrate theophylline".
- Section 6.4.3: Added "Guidance related to concomitant use of deferasirox with cholestyramine".
- Section 6.4.4: Added "Guidance related to concomitant use of deferasirox with drugs that have ulcerogenic potential".
- Section 6.6.4: Updated with "A signed Certificate of Destruction (or equivalent documentation as per local procedure) will be required for archiving in the Trial Master File".
- Section 7.1.3: Corrected to
 - "The planned duration of treatment in this study is for a maximum of 24 months".
 - "Treatment visits will commence at Visit 3 (Baseline). Patients will return to the site at 2 week intervals until Visit 5 (Month 1). Thereafter, scheduled visits will be monthly until EOT (Visit 28/Month 24)".
- Section 7.2.1: Corrected to "Serum ferritin testing will be performed at Screening Visit 1 and 2. Following enrolment (Visit 3/Day 1) serum ferritin will be tested at 2 week intervals until Visit 5 (Month 1). Thereafter, scheduled testing will be monthly".

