2.3 Rationale for dose and regimen selection

Deferasirox FCT is available in 3 dose strengths (90, 180 and 360 mg). In CICL670F2201, all ICT naïve patients randomized to the study received a deferasirox DT starting dose of 20 mg/kg/day, or the equivalent FCT starting dose of 14 mg/kg/day. All iron chelation pre-treated patients received deferasirox DT or an equivalent FCT starting dose corresponding to their pre-washout dose. In CICL670F2201, patients on DT formulation were allowed dose adjustments with \pm 5 to 10 mg/kg/day, but no more than 40 mg/kg/day while patients on FCT formulation were allowed dose adjustments with \pm 3.5 to 7 mg/kg/day, but no more than 28 mg/kg/day.

At the start of this study, the following will occur:

- Patients continuing directly from the CICL670F2201 study who were originally randomized to the deferasirox FCT formulation will continue treatment at the same dose they were assigned at the end of the CICL670F2201 study.
- Patients continuing directly from the CICL670F2201 study who were originally assigned to the deferasirox DT formulation will be switched to the deferasirox FCT formulation and will be assigned a deferasirox FCT dose equivalent to the deferasirox DT dose they were assigned at the end of CICL670F2201 study (Appendix 14.2).
- Patients completing the CICL670F2201 study who had switched to commercially available DT or other ICT will have to undergo a 5-day washout period and then use an equivalent FCT starting dose corresponding to their pre washout iron chelator dose.

Dose adjustment for better treatment effects based on serum ferritin levels and investigator's judgment, will be allowed if necessary every 3 months, with \pm 3.5 to 7 mg/kg/day, but no more than 28 mg/kg/day.

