7.1.3 Treatment period

The duration of study treatment in the current study is for a maximum of 24 months.

Treatment visits will commence at Visit 3 (Baseline). Patients will return to the site at 2 week intervals until Visit 5 (Month 1). Thereafter, scheduled visits will be monthly until EOT (Visit 28/Month 24).

Having completed the 24 weeks of CICL670F2201, patients recruited at Region Europe participating sites will be invited to continue FCT or switch from DT to the FCT formulation. Patients who completed CICL670F2201 but had switched to commercially available DT or other iron chelation will still be enrolled in the current study and receive FCT after a washout period.

All patients randomized in the DT arm in CICL670F2201 and well-managed on treatment with deferasirox DT will use an equivalent FCT dose. Patient switching from DT will use an equivalent FCT dose at the start of this study corresponding to their DT dose at the end of CICL670F2201 (see Appendix 14.2). A patient who is receiving an adjusted dose at the time of completing CICL670F2201 will commence this study receiving that adjusted dose until a time when it is deemed necessary to adjust the dose by the Investigator. Patients completing CICL670F2201 that had switched to commercially available DT or other ICT will have to undergo a 5-day washout period and then use an equivalent FCT starting dose corresponding to their pre-washout iron chelator dose.

Daily dose is calculated by the physician based on the patient's actual body weight.

For details on study design and dose adjustments, see Section 4 and Section 6.3. For details of assessments, see Table 7-1.

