1.1 Study design

This is an open-label, multicenter, single arm, phase III study aimed at collecting additional data on safety and tolerability as well as data on efficacy of the film-coated tablet (FCT) formulation in patients with transfusion-dependent thalassemia or myelodysplastic syndrome (MDS) (very low, low or intermediate risk) when treated for more than 24 weeks in CICL670F2201.

Patients from Region Europe participating sites in CICL670F2201who have completed the 24 week treatment period with ongoing tolerance to deferasirox (DFX) (in the investigator's opinion) and fulfilling all other eligibility criteria will be given the opportunity to continue study treatment and follow-up assessments in this study. This will include patients from Region Europe who completed 24 weeks of treatment with either DFX FCT or DFX dispersible tablet (DT) in CICL670F2201; and patients with a lag period between completion of CICL670F2201 and start of this study, i.e. those patients who completed CICL670F2201 and have already switched to commercially available DFX DT or another iron chelation therapy (ICT).

In CICL670F2201, iron-chelation naïve patients were assigned either DFX DT 20 mg/kg once daily or DFX FCT 14 mg/kg once daily. All iron chelation pre-treated patients were assigned a DFX DT or an equivalent FCT starting dose corresponding to their pre-washout dose. At the start of this study, the following was planned to occur:

- Patients continuing directly from CICL670F2201 who were originally randomized to the DFX FCT formulation will continue treatment at the same dose they were assigned at the end of CICL670F2201.
- Patients continuing directly from CICL670F2201 who were originally assigned to the DFX DT formulation will be switched to the DFX FCT formulation and will be assigned a DFX FCT dose equivalent to the DFX DT dose they were assigned at the end of CICL670F2201.
- Patients completing CICL670F2201 who had switched to commercially available DT or other ICT will have to undergo a 5-day washout period and then be assigned an equivalent FCT starting dose corresponding to their last DFX dose on CICL670F2201.

[figure not shown]
However, no patient for this study continued directly from CICL670F2201.

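### Protocol 2.3, 4.1 and 7.1.3 still start switchers on a different FCT dose from the one set in Section 6.1.1

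*Protocol*

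**What the plan says.** The patients concerned completed CICL670F2201, then took commercial DT or another chelator, and enter this study after a 5-day washout (switchers below).

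**Rule A, last CICL670F2201 dose.**
- Protocol 6.1.1: they "will then be assigned FCT at a starting dose equivalent to their last deferasirox dose on CICL670F2201".
- SAP 1.1: they will "then be assigned an equivalent FCT starting dose corresponding to their last DFX dose on CICL670F2201".
- Protocol Table 6-1, starting-dose column: "Described in Section 6.1.1 (see Appendix 14.2 for guidance".
- Protocol Table 7-1, footnote 11, refers study drug administration to Section 6.

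**Rule B, pre-washout chelator dose.**
- Protocol 2.3 and 4.1, in identical words: they "then use an equivalent FCT starting dose corresponding to their pre washout iron chelator dose".
- Protocol 7.1.3 (Treatment period): they "then use an equivalent FCT starting dose corresponding to their pre-washout iron chelator dose".

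The Amendment 1 rationale gives the purpose of the 6.1.1 change: "To clarify the following aspects in Section 6.1.1 (Dosing regimen)", with the item "Starting dose calculation for patients who completed CICL670F2201 study and switched to commercially available deferasirox dispersible tablet or other iron chelation therapy". The listed change is that these patients "will then be assigned FCT at a starting dose equivalent to their last deferasirox dose in CICL670F2201 study".

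**The concern.** Both rules stand in current text and cover the same patients, so this is not a difference between a change log and the live protocol. The log serves only as evidence of intent. It shows that the sponsor meant to settle this dose and wrote Rule A into 6.1.1. Its entries for 4.1 and 7.1.3 cover visit intervals, treatment duration and the study figure, and it lists no change to 2.3. This looks like a conforming change that was missed.

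At stake is the first dose a switcher receives. A site working from 7.1.3 could start a patient above or below the dose that 6.1.1 intends. Safety adjustments are allowed at any time, but 6.1.1 allows adjustment for better effect only every 3 months, so a low start could last about that long. Rule B also leaves a gap: Table 14-9 converts DT to FCT only, so a patient arriving on a non-deferasirox chelator has no tabulated FCT equivalent.

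**Working it through.** The plan states no figure to reproduce. The check compares the text and then sizes the gap from the protocol's own dosing tables.

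**Step 1. When the rules differ.** Table 14-9 pairs DT 5, 10, ..., 40 with FCT 3.5, 7, ..., 28 mg/kg/day, so FCT = 0.7 × DT. For a switcher to commercial DT, with both reference doses in DT terms:

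starting-dose gap (FCT) = 0.7 × (DT dose before washout − last CICL670F2201 dose)

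The gap is 0 if the dose did not change. One 5 mg/kg/day step gives 0.7 × 5 = 3.5 mg/kg/day. For a non-deferasirox chelator the gap cannot be calculated from the protocol.

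**Step 2. Size of one step.** No document gives doses after CICL670F2201, so the DT doses (20 to 40 mg/kg/day) and body weights (50 and 70 kg) are assumptions. Tablet doses are read from Tables 14-4 to 14-8.

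| Last dose as DT | Rule A FCT (mg/kg/day) | 3.5 as share of Rule A dose | Dispensed at 50 kg (mg) | Dispensed at 70 kg (mg) |
|---|---|---|---|---|
| 20 | 14 | 3.5/14 = 25.0% | 720 | 990 |
| 25 | 17.5 | 3.5/17.5 = 20.0% | 900 | 1260 |
| 30 | 21 | 3.5/21 = 16.7% | 1080 | 1440 |
| 35 | 24.5 | 3.5/24.5 = 14.3% | 1260 | 1710 |
| 40 | 28 | 3.5/28 = 12.5% | 1440 | 1980 |

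- One step at 50 kg: 180 mg/day throughout (for example 900 − 720).
- One step at 70 kg: 270, 180, 270 and 270 mg/day going down the column.
- Two steps at 50 kg: 360 mg/day (for example 1080 − 720).
- Two steps at 70 kg: 1440 − 990 = 450, 1710 − 1260 = 450 and 1980 − 1440 = 540 mg/day.

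**Step 3. Direction.** Below 28 mg/kg/day, Rule B can give more or less than Rule A. At 28 mg/kg/day the cap in 6.1.1 rules out a higher start, so the 12.5% figure is downward only.

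**Step 4. Reach.** SAP 1.1 says that no patient continued directly from CICL670F2201, and Table 7-1 footnote 1 assigns the washout to patients not continuing directly. Switching therefore looks like the main entry route. Protocol 2.2 and 5.1, however, only say that patients with a lag may enroll even if they had to switch. The number of switchers is not stated, nor is the number whose dose changed. The SAP's 58 is a planned maximum enrollment.

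**Step 5. Effect on the analyses.** SAP 2.6.2 and 2.8.2 are descriptive and test no hypotheses. The dose subgroups (SAP 2.2.1) and exposure summaries (SAP 2.5.1) use doses recorded on the dosing form. SAP 2.2 states that no deviation excludes a patient from an analysis set.

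**The case against.** The strongest reply is that the protocol already shows which rule governs. Table 6-1 sends the starting dose to 6.1.1, footnote 11 of Table 7-1 sends drug administration to Section 6, and SAP 1.1 repeats 6.1.1. Section 7.1.3 itself also ties the dose of patients switching from DT to their dose at the end of CICL670F2201. Sections 2.3 and 4.1 are rationale and design description, and a site with a patient on another chelator would be driven back to 6.1.1 anyway. Ferritin-based adjustment every 3 months can correct a mismatch early in a 24-month study.

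Most of this stands. It settles which rule to keep, leaves 7.1.3 as the main operative conflict, and limits how long a wrong start lasts. It does not cancel the sentence in 7.1.3, which is worded as a requirement for exactly these patients. The pointers to Section 6 are cross-references, and no clause says that 6.1.1 prevails.

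Three stronger readings are tempting, and the documents do not support them:
- *Every enrolled patient was dosed under conflicting rules.* Not continuing directly does not establish that a patient switched chelator, or that the dose changed.
- *The safety or ferritin results are biased.* The analyses describe patients at the doses recorded.
- *Sites following 7.1.3 will be misclassified as deviating.* SAP 2.2 gives only broad deviation categories. The full list is in the data review plan, which is not available here and may already name the standard.

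**Conclusion.** The inconsistency is certain and the intended rule is identifiable: 6.1.1. Sections 2.3, 4.1 and 7.1.3 were not aligned with it, and only 7.1.3 is a clearly operative treatment section. Where both reference doses are deferasirox doses and they differ, each 5 mg/kg/day DT step moves the starting FCT dose by 3.5 mg/kg/day, subject to the assumed doses and the cap described above. The number of patients affected is unknown and may be zero. No bias in the planned analyses follows. Severity is minor to moderate: it concerns a dosing instruction, but the other pointers favor 6.1.1 and the effect is confined to the starting dose.

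**What to change.** **Protocol.** At the next amendment, replace the pre-washout sentence in Sections 2.3, 4.1 and 7.1.3 with the 6.1.1 sentence. This also removes the missing conversion for other chelators. The cost is three sentences. Section 12.1 requires a written amendment with sponsor and ethics approval, and Health Authority approval where required, so the edit should ride on another amendment and not trigger one.

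**If all patients have already started.** SAP Amendment 1 is dated 26-Aug-19, before database lock, and reports in the past tense that no patient continued directly, so this is plausible. The protocol edit then cannot change doses given. Two steps remain useful before lock:
- Confirm in the data review plan that starting-dose deviations are judged against 6.1.1. If the plan already says so, nothing is needed.
- If the last CICL670F2201 dose can be retrieved, list each patient's starting FCT dose against its FCT equivalent and count the mismatches.

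The listing costs more than a single table. The SAP carries the formulation received in CICL670F2201 as a baseline variable but not the last dose, so a cross-study data pull may be needed. The patient number retained under Protocol 6.5.1 makes the link possible. No extra patients, visits or procedures are required.
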